#### 8.5 Titration Cycle Telephone Calls (Week 5)

On Days 6, 7, or 8 of Titration Cycles 2 (Week 5) after the start of the titrated doses, the study coordinator will call the participant for the following purposes:

- Verify the absence of ADRs
- Verify the absence of AEs
- Inquire about changes to concomitant medications/therapies and diet
- To answer any participant's questions and concerns

ADRs and changes to concomitant medications should be recorded in the participant's source documents. If the participant experiences ADRs, the PI should be consulted, and the appropriate procedures should be followed to adjust the study agent administration and down-titration, as needed and at the discretion of the PI (See sections [6.1.2-0](#)).

#### 8.6 Visit 4 and 5 Maintenance 1 and 2 (Weeks 8 and 12)

The following procedures will be performed during the maintenance phase:

- Conduct vitals (blood pressure, heart rate, respiratory rate, temperature), height, and weight
- Urine pregnancy test in females of childbearing potential
- Clinical laboratory samples, including CBC with differential, chemistry
- Administer patient- and parent-reported outcome questionnaires in person or through email or regular mail
- Assess AEs

- Assess changes to concomitant medication/therapies
- Assess participant compliance with diet
- Collect diet and medication log
- Collect study agent bottle and unused study agent dispensed at the previous study visit
- Dispense study agent supply with instructions
- Dispense diet and medication log
- Determine participant's compliance with study agent

The study staff will provide the participant with the monthly supply of the maintenance study agent, along with the study diary, and instructions. The study staff will instruct the participant to stop taking the study agent dispensed at the previous visit and to start taking the new supply of study agent upon receipt.

The visit window for Week 8 and 12 is  $\pm 7$  days; participants should be supplied with enough study agent to ensure continual administration of the study agent throughout the maintenance phase leading into the EOT Visit (Week 16).

#### 8.7 Monthly Telephone Calls (Maintenance Week 9 and 13)

On Days 6, 7, or 8 of Maintenance (Week 9 and 13) the study coordinator will call the participant for the following purposes:

- Verify the absence of ADRs
- Verify the absence of AEs
- Inquire about changes to concomitant medications/therapies and diet
- To answer any participant's questions and concerns

ADRs and changes to concomitant medications should be recorded in the participant's source documents. If the participant experiences ADRs, the PI should be consulted, and the appropriate procedures should be followed to adjust the study agent administration and down-titration, as needed and at the discretion of the PI (See sections [6.1.2-0](#)).

#### 8.8 Visit 6 End-of-Treatment (EOT) or Early Withdrawal (Week 16 $\pm 7$ days) Visit

For participants who have completed the maintenance phase or who have withdrawn early from the study, the following procedures will be performed in the clinic:

- Conduct vitals (blood pressure, heart rate, respiratory rate, temperature), height, and weight
- Physical exam
- Administer patient- and parent-reported outcome questionnaires
- Clinical laboratory samples, including CBC with differential, chemistry, and IgE
- Research laboratory samples

- Urine pregnancy test in females of childbearing potential
- Assess AEs
- Assess changes to concomitant medication/therapies
- Obtain esophageal biopsies including biopsies taken for clinical purposes and up to 4 biopsies from the distal esophagus for research purposes obtained from standard of care (SOC) endoscopy
- Assess participant compliance with diet
- Collect diet and medication log
- Collect study agent bottle and unused study agent
- Determine participant's compliance with the study agent

The EOT visit may be divided into two appointments, if necessary, in order to allow for all necessary procedures to be performed. Participants who have completed the maintenance phase should be instructed not to take the study agent on the day of this visit; the last dose of study agent should be taken the day prior to the EOT visit. If a participant withdraws from the study before completing the maintenance phase, the EOT/early withdrawal visit, including EGD and biopsy, should be conducted within one week of the participant's last dose of the study agent.

#### 8.9 Visit 7 Follow-Up Call/Visit (Week 20 ± 7 days)

The research personnel will conduct a follow-up safety telephone call to the participant 30 ± 7 days after the last dose of the study agent. Females of childbearing potential will have their urine pregnancy test conducted in the clinic. The call/visit will consist of the following procedures:

- Administer patient- and parent-reported outcome questionnaires
- Assess AEs
- Assess concomitant medications
- Assess diet and concomitant medication
- Urine pregnancy test in females of childbearing potential

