#### 11. Visit Windows

Study visits should take place within the time limits specified below: the designated visit windows for each scheduled visit are ±7 days of the week indicated on Table 4.

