g EndoFLIP is a SOCEvaluation for esophageal dysmotility, done at the same time as their endoscopy.

h The data gathered from these questionnaires will be correlated with several biomarkers of interest that have been associated with EoE. Each visit window (for visits 1-7) is  $\pm 7$  days.

i Urine pregnancy tests will be performed in females of childbearing potential on a monthly basis at each visit (except phone calls) and will be performed in the clinic.

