### 4. Follow-up after Early Study Withdrawal

Participants who withdraw prematurely from the study should have all EOT procedures (including a required urine  $\beta$ -hCG pregnancy test in all female participants of childbearing potential) performed at the time of withdrawal and should have a safety follow-up phone call 30 days after the last dose of the study agent.

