#### Study Therapy Regimen

Any event occurring within 30 days of end of treatment with study agent will be considered a possible adverse event and evaluated further for any relationship.

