## 6. Collecting and Recording of Adverse Events

### 1. Collection Period

AEs will be collected from the time after the participant signs informed consent/assent (Screening or Enrollment study visit) and will end after the cessation of the study agent (Week 20 [30 days after the last dose of the study agent]).

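### The only scheduled safety contact after end of treatment may fall on post-dose days 23 to 29, before the protocol's 30-day adverse-event period closes, and a competing Week 20 window can bring it earlier

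*Protocol*

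**What the plan says.** **AE period.** Section 11.3.1 of the protocol (Study Therapy Regimen) states: "Any event occurring within 30 days of end of treatment with study agent will be considered a possible adverse event". Section 11.6.1 says that collection "will end after the cessation of the study agent (Week 20 [30 days after the last dose of the study agent", which treats Week 20 and post-dose day 30 as the same date.

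**Visit 7.** Its timing is given in two ways.
- The text of Section 8.9 anchors it to the last dose: "follow-up safety telephone call to the participant 30 ± 7 days after the last dose of the study agent".
- The heading of Section 8.9 anchors it to the study week: "Visit 7 Follow-Up Call/Visit (Week 20 ± 7 days". Section 8.11 does likewise: "the designated visit windows for each scheduled visit are ±7 days of the week indicated on Table 4". Table 4 places Visit 7 at Week 20, and its footnote h ("Each visit window (for visits 1-7) is" ±7 days) names Visit 7 among the visits covered.

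**Early withdrawals.** Under Section 10.4 they "should have a safety follow-up phone call 30 days after the last dose of the study agent", with no window given.

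**Use of the data.** Section 3.3 makes any SAE or Grade 3 or higher AE a descriptive primary safety endpoint. The SAP (Variables of Interest) lists the rate of these events as its second primary outcome and states no observation period for it.

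**The concern.** Table 4 shows no scheduled contact after Visit 7. If the call is made before day 30, the remaining days still belong to the defined collection period, but no one is scheduled to ask about them. The loss cannot be repaired in the analysis. A late call does no harm, because Section 11.6.3 records onset dates and events can be cut off at day 30. An event that begins after an early call and is never volunteered cannot be recovered.

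A rate is easiest to interpret when every participant is asked about the same period. Here the solicited period depends on the calendar and on which of two windows the site follows. With 15 participants, one event more or less moves the proportion by 1/15, or 6.7 percentage points.

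The final urine pregnancy test is also tied to Visit 7, while inclusion criterion 6b (Section 4.2) requires contraception for at least one month after the last dose. The test can therefore precede the end of that month.

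**Working it through.** Days are counted with Week 0 as Day 0. Another origin shifts every date equally and leaves the intervals unchanged.

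**Inputs**
- EOT: "Visit 6 End-of-Treatment (EOT) or Early Withdrawal (Week 16" ± 7 days, Section 8.8), so Day 112 ± 7 = Day 105 to 119.
- Last dose for completers: the day before EOT (Section 8.8), so Day 104 to 118.
- Visit 7, week anchor: 20 × 7 ± 7 = Day 133 to 147.
- Visit 7, last-dose anchor: post-dose day 30 ± 7 = 23 to 37.
- End of AE period: post-dose day 30.

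**1. The plan's own equation of Week 20 with 30 days.** On the nominal schedule the last dose is on Day 111 and Week 20 is Day 140. 140 − 111 = 29 days. The stated 30 is reproduced to within one day, but the exactly on-schedule contact is itself one day short.

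**2. Last-dose anchor (Section 8.9 text).** Days 23 to 29 are 7 of the 15 permitted days. Largest gap: 30 − 23 = 7 days, which is 7/30 = 23% of the post-dose period.

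**3. Week anchor alone (8.9 heading, 8.11, Table 4).** Post-dose day of contact = Visit 7 day − last-dose day.

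| EOT | Last dose | Earliest | Latest |
|---|---|---|---|
| Day 105 | Day 104 | 133 − 104 = 29 | 147 − 104 = 43 |
| Day 112 | Day 111 | 133 − 111 = 22 | 147 − 111 = 36 |
| Day 119 | Day 118 | 133 − 118 = 15 | 147 − 118 = 29 |

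The earliest permitted contact is before day 30 for every permitted EOT day. Largest gap: 30 − 15 = 15 days (15/30 = 50%). With EOT on Day 119, post-dose day 30 is Day 148, one day after the window closes.

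**4. Both windows required.** The contact must fall on days 29 to 37 (EOT Day 105), 23 to 36 (Day 112) or 23 to 29 (Day 119). A call that meets both rules fails to reach day 30 altogether only for EOT on Day 119. With EOT on Day 118, 147 − 117 = 30, so day 30 is just reachable.

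**5. Scale.** From Day 0 to post-dose day 30 on the nominal schedule is 111 + 30 = 141 days, so a 7-day gap is 7/141 = 5% of that time. As an illustration, assume that the 4.6% SAE frequency quoted in Section 1.5 for losartan in the paediatric proteinuria trial applies over 12 weeks (84 days) at a constant rate, and that all 15 participants are called on day 23. The expected number of SAEs in the gap is 15 × 0.046 × 7/84 = 0.06. With a 15-day gap for all it is 15 × 0.046 × 15/84 = 0.12. The documents give no comparable rate for non-serious Grade 3 or higher AEs.

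**The case against.** **Day 15 is not what the stated rule allows.** A reader might infer from the Week 20 window that calls between days 15 and 29 are simply permitted. A day-15 call would breach the 30 ± 7 sentence in the same section. It arises only if the week anchor is used alone and EOT falls on its last permitted day. Table 4 footnote b, which limits time on each dispensed supply to 28 days at monthly and titration visits, may exclude that case. If it also governs EOT, four supplies end dosing by about Day 112, and the week window then opens at about 133 − 112 = day 21. The ± 7 days for EOT in Section 8.8 points the other way, and the documents do not settle it. This objection stands: the firm figure is days 23 to 29.

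**The gap is not blind.** It is tempting to say that the days are unobserved and that non-serious Grade 3 or higher events have no route in. The documents do not support that. Participants are told to call about adverse events (8.2), unscheduled visits are provided for (8.10), unsolicited complaints count as a source (11.6.2), and other reportable AEs must be entered once the site learns of them (11.7). Late SAEs remain reportable (11.7), and Sections 10.1 and 16.10 expect data up to 30 days after the last dose. What remains is that none of these is a scheduled enquiry, and the late-reporting provision covers SAEs only.

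**Early withdrawals already have an anchor.** One might read Section 10.4 as a third conflicting rule. It uses the last dose and shares its centre with 30 ± 7. It lacks only a window.

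**A symmetric ± 7 days is the house rule for visits.** True, but this contact closes a fixed 30-day period, so days early and days late do not have the same consequence.

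**Conclusion.** The plan defines a 30-day post-dose AE period and lets its only scheduled post-EOT enquiry end before that period does. The shortfall is up to 7 days under the stated 30 ± 7 rule, and up to 15 days if the conflicting Week 20 window is applied alone with EOT on Day 119. The two windows also disagree with each other, and the equation of Week 20 with 30 days is one day out even on schedule.

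The consequence is uneven solicited follow-up and a possible loss of events, mainly non-serious Grade 3 or higher AEs. A reader might go further and conclude that the reported rate will be too low. The documents show only that missed events would push it in that direction. The endpoint is descriptive, about 15 participants are planned, passive reporting continues, and the expected number of events in the gap is small. This is a worthwhile and inexpensive correction, and it does not threaten the trial's conclusions.

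The figures assume completers who take the last dose the day before EOT and visits held within the stated windows.

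**What to change.** - In Sections 8.9, 8.11, 10.4 and 11.6.1, and in Table 4 with its footnotes, anchor Visit 7 and the end of AE collection to the last dose for all participants, completers and early withdrawals alike.
- Remove Week 20 as a competing anchor, including from the clause in 11.6.1 that equates it with 30 days.
- Set the AE contact window at day 30 to day 37 after the last dose. If a call is made earlier, add a brief AE re-contact at or after day 30 before collection is closed.
- Reconcile the timing of the final pregnancy test at Visit 7 with the one-month contraception requirement in inclusion criterion 6b.

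The cost is a few lines of protocol text and small changes to Table 4. Some calls, and the patient-reported outcomes collected at them, will take place up to a week later.

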#### 10. Unscheduled Visits

If disease activity increases or other concerns arise between regularly scheduled visits, participants should be instructed to contact study personnel and may be asked to return to the study site for an "unscheduled" visit. Unscheduled visits will take place for an unexpected pregnancy or any complication or AE/SAE that requires an extra visit. The procedures to be performed at the unscheduled visits will be at the discretion of the PI. These visits will be documented in the source document and the unscheduled visit case report.

#### 11. Visit Windows

Study visits should take place within the time limits specified below: the designated visit windows for each scheduled visit are ±7 days of the week indicated on Table 4.

8.12 Table 4: Study Design and Schedule of Assessments

PHASE	PRE-TREATMENT PHASE	Titration Phase a,c		TREATMENT PHASE			EOT or Early Withdrawal	FOLLOW-UP PHASE	
	1	2	2a	3	Maintenance Phase				6
Visit Number	1	2	2a	3	3a	4	5	6	7
Visit Description	Screening	Enrollment Baseline	Week 1 Visit Check BP/AEs	Visit 3 Up-titration	Phone call	Maintenance Month 2	Maintenance Month 3	EOT Visit	Safety Phone call
Week	-12 to 0	0	1	4	5	8	12	16	20
Perform informed consent/assent	X								
Assess eligibility (inclusion/exclusion criteria)	X	X							
Obtain medical, surgical, dietary history, & demographics	X								
Vitals (height, weight, blood pressure, heart rate, respiratory rate, temperature)	X	X		X		X	X	X	
Physical exam	X			X				X	
SOCEGD with biopsies/EREPS	X a							X	
EndoFLIP e	X							X	
PedsQL™ EoE Module h		X		X		X	X	X	X
FEESV 2.0 i		X		X		X	X	X	X
EESal		X		X		X	X	X	X
EoE-QoL-Adult		X		X		X	X	X	X
Participant Intake Form		X							
Clinical laboratory samples	X			X		X	X	X	
Research laboratory samples	X d							X d	
Urine pregnancy test l	X			X		X	X	X	X
Assess AEs		X	X	X	X	X	X	X	X
Assess concomitant medications and/or therapies		X	X	X	X	X	X	X	X
Dispense study drug, drug diary, and instructions		X		X		X	X		
Determine compliance with study drug				X		X	X	X	
Collect unused study drug				X		X	X	X	

a First EGD used to determine eligibility may be conducted within 12 weeks prior to enrollment visit.

b At each monthly or titration visit, the participant must have been on previously dispensed dose of study drug for at least 21 days but no more than 28 days.

c Clinical labs: CBC with differentials, chemistry panel, and IgE (first and last visit only).

d Research labs: mRNA in blood and tissue, TGF- $\beta$  in blood and tissue.

e In addition to assessing diet and concomitant medication compliance at each scheduled visit, research personnel will also conduct one telephone call per month to assess compliance during the maintenance phase. During the titration phase, diet and concomitant medication compliance will be conducted during scheduled phone calls (Visits 2a and 3a).

f Participants who withdraw from the study before completing the maintenance phase should complete the EOT/early withdrawal visit, including SOCEGD and biopsy, within two weeks of the last dose of study drug.

g EndoFLIP is a SOCEvaluation for esophageal dysmotility, done at the same time as their endoscopy.

h The data gathered from these questionnaires will be correlated with several biomarkers of interest that have been associated with EoE. Each visit window (for visits 1-7) is  $\pm 7$  days.

i Urine pregnancy tests will be performed in females of childbearing potential on a monthly basis at each visit (except phone calls) and will be performed in the clinic.

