### 2. Inclusion Criteria

Participants must meet all of the following inclusion criteria to be eligible for participation in this study.

1. Written informed consent has been provided by the participant /parent or legal guardian.
2. Participants (of any gender and any race) aged  $\geq 5$  years to  $\leq 25$  years at time of screening.
3. The participant has confirmed, active EoE (within 12 weeks prior to enrollment) as defined by esophageal mucosal eosinophils  $\geq 15$  per HPF (400 x magnification) confirmed by the research pathologist AND fits into one of the following categories:
  - a. Participant has not been diagnosed with and does not display phenotypes suggestive of a CTD, or
  - b. Participant has been diagnosed with a CTD (e.g., MFS, LDS, EDS, or hypermobility syndromes).
4. The participant has been on a high dose of PPI (at least one dose, once daily) for at least 8 weeks prior to a diagnostic endoscopy of EoE without histologic resolution (i.e.,  $\geq 15$  eosinophils/HPF). Due to the variety of doses and various PPIs available, the dose will be confirmed adequate at the discretion of the site PI.  
Note: Participants may continue with their acid reflux therapy as long as the dose remains the same throughout the study.
5. Participant must maintain the same diet, swallowed steroid, and PPI therapies throughout the duration of the study. Participants with active EoE on these therapies may be included in the study, as long as they agree to maintain the same diet, swallowed steroid, and PPI therapies.
6. At the time of study entry, a female participant is eligible if she meets one of the following criteria:

- a. Is of non-childbearing potential (pre-menarchal or surgically sterile with documentation);
- b. Is of childbearing potential with a negative urine pregnancy ( $\beta$ -hCG) prior to enrollment into the study (i.e., at screening) and at each study visit. Subsequently, these participants must agree to use adequate birth control measures (e.g., condom, oral / injectable / subcutaneous contraceptives, intrauterine device, or sexual abstinence) during the study and for at least one month after the last dose of study drug, which will be documented in the source documents.

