## 8 Study Procedures

### 1. Visit 1 Screening/ Baseline Visit (Week -12 to 0)

#### Recruitment

The research study will be explained in lay terms to each potential research participant. Participants will be recruited from the gastroenterology, allergy, or other clinics at each study site when potential participants with EoE and CTD may be seen. Participants who receive care from other institutions that express interest in participating may be enrolled in the study. The PI and the study staff team will work with the participant's primary care physician to explain the study objectives and requirements for the study. If the participant's primary care physician agrees that the participant would be a good candidate for the study, study staff will contact the participant and carry out all recruitment and screening procedures. In addition, potential participants will be identified through the EGD database (CCHMC IRB studies #2008-0090 and 2008-0098), as well as other databases and resources at each study site. Research staff will pre-screen or identify potentially eligible participants by conducting a review of existing medical and/or research records and IRB-approved recruitment materials.

The clinical trial information will be entered into a databank on [www.clinicaltrials.gov](http://www.clinicaltrials.gov) maintained by the U.S. National Library of Medicine (NLM) at the National Institutes of Health (NIH) or other websites.

The purpose of the screening period is to confirm eligibility to participate in the study. The screening visit should occur at a maximum of 12 weeks prior to the enrollment visit. The research staff member will perform the informed consent process according to Section 19. After obtaining informed consent, the following study assessments/procedures should be performed and documented up to 12 weeks prior to the enrollment (Week 0) visit or during the enrollment visit:

- Eligibility (inclusion and exclusion criteria)
- Medical, surgical and diet history
- Conduct vitals (blood pressure, heart rate, respiratory rate, temperature), height, and weight
  - Demographics (age, gender, race)
  - Physical exam performed by a study clinician
  - Clinical laboratory samples, including CBC with differential, chemistry, and IgE
  - Research laboratory samples (See Table 4)
  - Urine pregnancy test for females of childbearing potential
  - Concomitant medications and therapies

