## 8.2 Visit 2 Enrollment / Titration Cycle 1 / (Week 0)

All eligible participants will be enrolled into the study at Week 0 if they meet all eligibility criteria and have completed the screening procedures. Screening and enrollment visits may be combined when deemed necessary. If the screening and enrollment visit are combined, the study drug will not be dispensed until all inclusion and exclusion criteria have been met and all screening visit procedures have been performed. This includes the review of all laboratory tests performed during the screening portion of the visit. If a participant is screened and enrolled within a 5-day time frame, study procedures that would be repeated will only be performed once. The enrollment visit also marks the beginning of the Treatment Phase and Titration Cycle 1. At this visit, staff members will:

- Reassess eligibility (inclusion and exclusion criteria)
- Conduct vitals (blood pressure, heart rate, respiratory rate, temperature), height, and weight
- Administer patient- and parent-reported outcome questionnaires
- Urine pregnancy test in females of childbearing potential
- Assess and inquire about AEs
- Assess concomitant medications and/or therapies
- Assess participant compliance with diet
- Dispense study agent with instructions

- Dispense diet and medication log

The PI or the sub-investigator will determine the initial dose of study agent per the titration schedule in Sections [6.1.2 - 0](#). The participant's weight obtained at this visit will be used to calculate the initial dose of losartan. The Investigational Pharmacy will dispense the appropriate dose and amount of the study agent per the Manual of Operations (MOO). The participant will be instructed to administer the study agent orally once daily, at approximately the same time each day, with or without food, for at least 21 days but less than 28 days. The participant will also be instructed to record the start and stop date of the study agent and each dose in the study diary. The participants will be instructed to call the PI and/or study coordinator if they have any questions, concerns, adverse events, or changes in medication.

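### Table 4 leaves the urine pregnancy test unmarked at the first-dose visit, contradicting Section 8.2, the table's own footnote and criterion 6b

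*Protocol*

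**What the plan says.** All of the relevant text is in the Protocol.

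- **Section 8.2, Visit 2 (Week 0).** The staff list includes "Urine pregnancy test in females of childbearing potential" and, further down, "Dispense study agent with instructions". Eligibility is reassessed at the same visit. If screening and enrollment fall within 5 days of each other, procedures that would be duplicated are done once.
- **Section 8.12, Table 4, grid.** The pregnancy-test row has marks at Visits 1, 3, 4, 5, 6 and 7. The cells for Visits 2, 2a and 3a are empty.
- **Table 4, pregnancy-test footnote.** Tests are done "on a monthly basis at each visit (except phone calls) and will be performed in the clinic".
- **Section 4.2, criterion 6b.** A negative test is needed "prior to enrollment into the study (i.e., at screening) and at each study visit". The Synopsis version differs only in saying each monthly study visit.
- **Section 8.1.** "The screening visit should occur at a maximum of 12 weeks prior to the enrollment visit". The screening procedures, which include the pregnancy test, may be done at any time in those 12 weeks or at the enrollment visit itself.
- **Table 4, first footnote.** "First EGD used to determine eligibility may be conducted within 12 weeks prior to enrollment visit". This concerns the endoscopy only.

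**The concern.** Visit 2 is the last point at which a pregnancy can be found before exposure begins. Pregnancy is exclusionary (criterion 15), and Section 5.3 treats fetal exposure to losartan as a high-risk problem. Yet the assessment schedule shows no test at that visit, while three other statements in the same document call for one.

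If site staff use the grid as their checklist, the only test behind the first dose is the screening test, and a pregnancy beginning in the screening interval would be missed. Section 5.2 ties fetal injury to second- and third-trimester exposure and says that exposure limited to the first trimester does not appear to cause it. How late a missed pregnancy is found therefore matters.

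**Working it through.** The plan states no figure to reproduce. The check is to line up the table row with the visits, then work out the oldest result that could support the first dose under each statement.

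**1. The row.** Table 4 has nine visit columns: 1, 2, 2a, 3, 3a, 4, 5, 6, 7. The pregnancy-test row has nine cells: mark, empty, empty, mark, empty, mark, mark, mark, mark. Neighboring rows (eligibility, vitals, dispensing) put their Visit 2 marks in the second cell, so the alignment looks sound.

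**2. Which empty cells are explained.** Another Table 4 footnote treats Visits 2a and 3a as phone calls, so the phone-call exception accounts for them. Visit 7 is headed as a phone call but is marked; Section 8.9 explains that this test is done in the clinic. Visit 2 is a clinic visit, and nothing explains its empty cell.

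**3. Age of the last result at first dose.**

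| Statement | Test at Visit 2? | Oldest result |
|---|---|---|
| Section 8.2 with its 5-day rule | Yes | 0 to about 5 days |
| Table 4 footnote | Yes | 0 days |
| Criterion 6b, Section 4.2 | Yes, as a study visit | 0 days |
| Criterion 6b, Synopsis | Yes, if Week 0 counts as a monthly visit | 0 days |
| Table 4 grid alone | Not marked | 12 × 7 = 84 days |

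If the ±7-day visit window were added to the 12-week limit, which is an assumption, the last figure would be 84 + 7 = 91 days.

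**4. Next marked test.** Visit 3 follows at least 21 days of dosing, with an upper limit of 28 days. Under the grid alone, consecutive tests could be 84 + 21 = 105 to 84 + 28 = 112 days apart, or 15 to 16 weeks.

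**5. When the empty cell is harmless.** If screening and enrollment are combined, or fall within 5 days, one test serves both visits. The discrepancy matters only when they are further apart.

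**6. Which result counts.** Criterion 6b names the screening test as the pre-enrollment one, then asks for tests at study visits as well. Section 8.2 withholds drug until screening procedures and laboratory review are complete, but that sentence is written for combined visits. For separate visits, no passage says which pregnancy result supports the eligibility reassessment, or that dispensing waits for the Visit 2 result.

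**The case against.** The strongest reply is that only one cell is out of line. Section 8.2, the footnote and criterion 6b all lead to a test at Visit 2, and the Synopsis wording is compatible with one because Week 0 belongs to the series of Weeks 0, 4, 8, 12 and 16. The footnote is part of Table 4, so a site reading the whole table would still test. Criterion 6b also requires contraception, and criterion 15 excludes anyone of childbearing potential who is not using an effective method.

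Most of this stands, and it rules out two stronger readings. A reader might infer that the Protocol allows losartan to be started on a 12-week-old test. It does not: that takes the grid cell by itself, against the footnote, Section 8.2 and the second half of criterion 6b. A reader might also infer that a Visit 2 test has no bearing on eligibility. That overlooks the study-visit wording in criterion 6b, the exclusion for pregnancy and the reassessment at Visit 2.

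The reply does not remove the discrepancy. The grid still disagrees with the text at the visit where exposure starts, and the contraception requirements do not replace a test. The table was read from PDF by a program, and the row's footnote marker prints as a different letter from the note, so the empty cell should be confirmed against the source document.

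**Conclusion.** The point holds as an internal inconsistency with a safety consequence. Table 4 omits, at the first-dose visit, a test that Section 8.2, the table's own footnote and criterion 6b call for. The last result before dosing is 0 to about 5 days old under Section 8.2 and up to 84 days old under the grid alone. The larger figure describes what could happen at a site using only the grid, with screening at the 12-week limit; it is not what the Protocol authorizes.

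A second, smaller gap remains however the cell is read: for separate visits, the Protocol does not say which pregnancy result supports the Visit 2 eligibility decision. Both conclusions assume that the extracted row is faithful to the source. The 12-week endoscopy window plays no part in them, since the relevant limit is the one on the screening visit in Section 8.1.

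**What to change.** Reconcile the Visit 2 cell of Table 4 with Section 8.2, the pregnancy-test footnote and both versions of criterion 6b, so that one statement governs testing at the first-dose visit and the grid matches it. State which result supports the eligibility reassessment at Visit 2, and how the hold on dispensing applies when screening and enrollment are separate visits. The choice of clinical rule is for the sponsor and investigators; none is proposed here.

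The cost is one table cell and a few sentences in a protocol amendment. Because Section 8.2 already lists the test, no procedure is added. The sample size and the analysis are unaffected.
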